12.5.2 Key Secondary Endpoint Sample Size

The null hypothesis is that there is no difference in progression free survival (PFS) between cobomarsen and vorinostat. A sample size of 126 subjects (63 per group; 66 events) provides at least 80% power to detect a difference between vorinostat and cobomarsen, assuming a median PFS of 4 months for vorinostat and 8 months for cobomarsen. This calculation is based on a one-sided, logrank test at the 0.025 level of significance, assuming 15 months of recruitment, 6 months of follow-up, and 17% censoring. No interim analysis is planned for PFS.

12.6 Measures to Minimize Bias

12.6.1 Randomization Procedures

The randomization will be stratified based on subjects with at least one skin tumor at Screening vs. no skin tumors at Screening. Subjects will also be stratified based on prognostic factors (age at diagnosis > 60 years and LDH level > ULN at diagnosis) ([Scarisbrick et al. 2015](#)). Subjects will be stratified based on 0-1 vs 2 of these prognostic factors.

12.6.2 Evaluation of Success of Blinding

Not applicable

12.6.3 Breaking the Study Blind

Not applicable

13 DATA HANDLING AND RECORD KEEPING

13.1 Study Files and Subject Source Documents

The investigator must maintain adequate and accurate records to enable the conduct of the study to be fully documented and the study data to be subsequently verified. These documents include the subject's clinical source documents and Investigator's Study Files.

Subject clinical source documents may include, but are not limited to, hospital/clinic records, physician's and nurse's notes, appointment book, original laboratory reports, ECG, radiograph, pathology and special assessment reports and consultant letters.

The investigator will ensure the Study Files are maintained, including the eCRFs and query forms, protocol/amendments, IRB/IEC and regulatory approvals with associated correspondence, signed ICFs, study treatment records, staff curriculum vitae and authorization forms, all

correspondence and other appropriate documents. Such data shall be secured in order to prevent loss.

The investigator will allow personnel authorized by the Sponsor access to all study data at any time.

13.2 Data Collection Methods

Data collection is the responsibility of the clinical trial staff at the site under the supervision of the site Investigator. The investigator is responsible for ensuring the accuracy, completeness, legibility, and timeliness of the data reported. An eCRF must be completed for each person who signs informed consent, regardless of the duration of their trial participation.

All source documents should be completed in a neat, legible manner to ensure accurate interpretation of data. When making changes or corrections, cross out the original entry with a single line, and initial and date the change. **DO NOT ERASE, OVERWRITE, OR USE CORRECTION FLUID OR TAPE ON THE ORIGINAL.** Documents (including laboratory reports, hospital records subsequent to SAEs, etc.) transmitted to the CRO or the Sponsor should include the assigned subject identifier but should not include the subject's name in order to ensure confidentiality.

Electronic CRFs will be provided for recording data for each subject enrolled in the study. Data reported in the eCRF derived from source documents should be consistent with the source documents or the discrepancies should be explained and maintained in the subject's official electronic study record. The Investigator should consult the eCRF completion guidelines for comprehensive instructions for completing the eCRF.

Clinical data will be entered into a 21 CFR Part 11-compliant electronic data capture system, unless otherwise specified. The data system includes password protection and internal quality checks, such as automatic range checks, to identify data that appear inconsistent, incomplete, or inaccurate. Clinical data will be entered directly from the source documents.

13.3 Retention of Records

All clinical study documents must be retained by the investigator until at least 2 years after the last approval of a marketing application in an International Conference on Harmonization (ICH) region and until there are no pending or contemplated marketing applications in an ICH region; or, if no application is filed or if the application is not approved for such indication, until 2 years after the investigation is discontinued and regulatory authorities have been notified.

Investigators may need to retain documents longer if required by applicable regulatory requirements or if requested by the Sponsor. The investigator must notify the Sponsor prior to destroying any clinical study records. Should the investigator wish to assign the study records to another party or move them to another location, the Sponsor must be notified in advance. It is the responsibility of the Sponsor to inform the investigator when these documents no longer need to be retained.

If the investigator cannot guarantee this archiving requirement at the study site for any or all of the documents, special arrangements must be made between the investigator and miRagen to securely store the documents in an off-site storage location so that they can be returned to the investigator in case of a regulatory audit. Where source documents are required for the continued care of the subject, appropriate copies should be made for off-site storage.

13.4 Protocol Deviations

The investigator and the study site staff are responsible for ensuring the study is conducted in accordance with the schedule of procedures and assessments described in this protocol and in accordance with Good Clinical Practice (GCP). The site must use continuous vigilance to identify and document any deviations that occur. All deviations must be reviewed by the investigator to assess whether the safety of study participants or study integrity has been affected by the deviation.

Intentional deviations from the protocol shall not be made except in a medical emergency, when the intent is to reduce immediate risk to the subject. In such cases, the Sponsor, CRO, the IRB/IEC and regulatory authorities, as appropriate, should be notified, in accordance with local requirements. In all other cases, the nature of the deviation, the justification for the deviation, and prior written approval of the Sponsor must be documented.

Under no circumstance should the investigator contact the Sponsor or designee monitoring the study, to request approval of a protocol deviation, as no authorized deviations are permitted.

Changes to the protocol may be made only when a written substantial protocol amendment has been approved by the Sponsor and submitted to the IRB/IEC and applicable regulatory agencies in accordance with local requirements. Appropriate approval(s) must be obtained before changes can be implemented.

14 QUALITY CONTROL AND QUALITY ASSURANCE

Quality Control procedures will be implemented beginning with the data entry system, and data quality control checks will be run on the database. Any missing data or data anomalies will be communicated to the site(s) for clarification/resolution.

The Sponsor (or designee) is responsible for ensuring the proper conduct of the study with regard to protocol adherence and validity of data recorded in the eCRFs by assigning CRAs to each site. The CRA is responsible for reviewing the eCRFs at regular intervals throughout the study, verifying adherence to the protocol, assuring completeness, consistency and accuracy of the data, and reviewing study files and drug accountability. The data will be verified against the original medical records and laboratory results as part of source document verification to ensure validity of the data. The investigator's responsibility is to ensure that any issues detected in the course of a monitoring visit are resolved.

To ensure compliance with GCP and all applicable regulatory requirements, a quality assurance audit may be conducted by the Sponsor or the Sponsor's designee. Regulatory agencies may also conduct a regulatory inspection of this study. Such audits/inspections can occur at any time during or after completion of the study. If an audit or inspection occurs, the investigator and institution agree to allow the auditor/inspector direct access to all relevant documents and to allocate his/her time and the time of his/her staff to the auditor/inspector to discuss findings and any relevant issues.

The investigator and study staff are responsible for maintaining a comprehensive and accurate filing system of all study-related documentation that will be suitable for inspection at any time by the Sponsor, its designees, and/or regulatory agencies (see [Section 13.3](#)). In signing this protocol, the investigator understands and agrees to give access to the necessary documentation and files.

15 ETHICS/PROTECTION OF HUMAN SUBJECTS

This Section 15 of the Clinical Trial Protocol is subject to the terms of the Clinical Trial Agreement between miRagen Therapeutics, Inc. and the study centers. In the event of a discrepancy between the Clinical Trial Agreement and this Clinical Trial Protocol, the terms of the Clinical Trial Agreement shall control.

15.1 Ethical Conduct of the Study

This study will be conducted in compliance with the ICH GCP guidelines, US regulations for the ethical conduct of clinical studies under 21 Code of Federal Regulations (CFR; Parts 50, 56 and 312), the European Clinical Trials Directive 2001/20/EC and implementing national regulations, the European Clinical Trials Regulation No. 536/2014, the Declaration of Helsinki, and with ICH guidelines regarding scientific integrity (E4, E8, E9 and E10). This study will also adhere to all FDA, state and local regulatory requirements, and requirements for data protection.

15.2 Institutional Review Board/Independent Ethics Committee Review

Before trial initiation, the investigator and institution must have written and dated approval from an accredited IRB/IEC for the study protocol, written ICF, subject recruitment procedures (e.g., advertisements), and any written information to be provided to subjects. Any amendment to the protocol will require review and approval by the IRB/IEC before the changes are implemented to the study. All changes to the consent form will be IRB/IEC approved prior to implementing the change; a determination will be made regarding whether previously consented subjects need to be re-consented using the amended form.

Appropriate reports on the progress of the study will be made by the investigator to the IRB/IEC and the Sponsor in accordance with applicable regulations. All correspondence with the IRB/IEC should be retained in the investigator's Study File. Copies of IRB/IEC approvals should be forwarded to miRagen or its designee.

15.3 Informed Consent Process

An ICF template will be provided by the Sponsor to the investigator for submission to the IRB/IEC. Any site-specific changes to the ICF must be approved by the Sponsor prior to its submission to the IRB/IEC. The ICF must be approved by the IRB/IEC prior to being presented to potential study subjects.

Individuals may agree to participate in the clinical trial only after the risks and possible benefits of their participation have been explained and extensively discussed. The investigator will explain the purposes, procedures, and potential risks of the research study in terms suited to their comprehension, as well as their rights as a research subject. Subjects will have the opportunity to carefully review the written ICF, discuss the study with their surrogates, and ask questions prior to signing. Written informed consent must be obtained from each study subject or his/her legally acceptable representative prior to conducting any study-related procedures.

The investigator must use the most current IRB/IEC-approved ICF for documenting written consent. Each informed consent will be appropriately signed and dated by the subject or the subject's legally acceptable representative and by the person obtaining consent. The site must retain the original signed ICF and provide a copy to the subject.

15.4 Confidentiality of Information

Individual subject medical information obtained as a result of this study is considered confidential. The investigator and the study center will adhere to all applicable laws relating to the protection of subject information. To assure that subject confidentiality is maintained, subject data will be identified only by a study-assigned number on any Sponsor forms, reports, publications, or in any other disclosures, except where required by law.

All personnel of miRagen Therapeutics, Inc. and its designees with access to the primary study data will handle subject data in a confidential manner in accordance with applicable regulations governing clinical research. Subject records will be inspected only in connection with this research project. Information generated as a result of a subject's participation in this study may be disclosed to third parties for research, regulatory, and other purposes in any country as determined by miRagen Therapeutics, Inc. However, subjects will not be individually identified but will be referred to by the study-assigned number.

15.5 Future Use of Stored Specimens

Laboratory data collected for this study will be analyzed and stored at the central laboratory.

With the subject's approval and as approved by local IRBs, de-identified biological samples will be stored at the central laboratory for up to 2 years after the completion of the study. These samples could be used for future research performed by miRagen or its collaborators into the causes of MF, its complications, and other conditions for which individuals with MF are at increased risk, and to improve treatment.

16 PUBLICATION POLICY

Publication and/or disclosure of information or data related to this Clinical Trial Protocol is subject to and governed by the Clinical Trial Agreement between miRagen Therapeutics, Inc. and the study center to which the Principal Investigator is a signatory.

After conclusion of the study, investigators in this study may make oral presentations of study results or publish such results in scientific journals or other scholarly media without prior written approval from miRagen Therapeutics, Inc., only after the following conditions have been met:

- The results of the study in their entirety have been publicly disclosed by or with the consent of miRagen Therapeutics, Inc. in an abstract, manuscript or presentation forum;
- The investigator has complied with the terms of the Clinical Trial Agreement and all requests from miRagen Therapeutics, Inc. to delete any references to its confidential information (other than study results);
- The study has been completed at all study sites for at least 1 year.

Appendix A. Schedule of Events (Screening, Randomized Period)

Study Procedure or Assessment (completed after obtaining informed consent from the patient).	Screening ^a	
	Weeks Prior to Randomization	Time of Randomization
Study Day Prior to Randomization	-4	Day -3 to -1
	-28 to -3	Day -3 to -1
Registration in Interactive Web Response System	X	X ⁱ
Modified Severity Weighted Assessment Tool (mSWAT)	X	
Medical History and Concomitant Medications ^b	X	
Report Prior CTCL Treatments	X	
ECOG Performance Status	X	
Vital Signs	X	
Complete Physical Examination Including Weight and Height	X	
Triplicate 12-lead Electrocardiogram ^c	X	
Radiological Imaging (CT/MRI Scans) ^d	X	
HIV, Hepatitis B, Hepatitis C Screening ^e	X	
Follicle-stimulating Hormone ^{e, f}	X	
Serum Pregnancy Test ^e	X	
Hematology, Chemistry, Coagulation and TSH ^e	X	
Urinalysis with Microscopy ^e	X	
Flow Cytometry and CBC (performed by the local laboratory) ^g	X	
Review Inclusion/Exclusion Criteria	X	X (RECONFIRM)
Confirm CTCL Staging based on Screening Assessments		X
Initiate Medical Monitor Review after all Screening Data are Entered in the eCRF ^h		X
Adverse Events	Review on an ongoing basis	

Abbreviations: CT = computed tomography; CTCL = cutaneous T-cell lymphoma; ECG = electrocardiogram; ECOG = Eastern Cooperative Oncology Group; eCRF = electronic case report form; HIV = human immunodeficiency virus; IWRS = Interactive Web Response System; MRI = magnetic resonance imaging; mSWAT = Modified Severity Weighted Assessment tool; TSH = thyroid-stimulating hormone

a) Subjects who do not meet the inclusion/exclusion criteria may rescreen once at the discretion of the Investigator.

- b) All medications (including over-the-counter medicines, herbal treatments, supplements, and vitamins) administered 30 days before the first administration of study treatment (Day 1) until the end of the study should be recorded on the eCRF.
- c) Triplicate 12-lead ECGs (3 serial ECGs conducted within approximately 5-10 minutes total time).
- d) CT/MRI scans collected by the local site and sent to the Central Laboratory for confirmation.
- e) Collected by the clinical site, processed and sent to the central laboratory. Coagulation includes prothrombin time, partial thromboplastin time, and international normalized ratio.
- f) Only for women who are not surgically sterile as confirmation of menopause (for subjects whose last menstrual cycle was within the last year).
- g) Flow cytometry and CBC performed by the site's local laboratory. Panels must include antibodies to CD3, CD4, CD8, CD26, CD45 and CD7.
- h) To occur prior to initiating randomization procedures in IWRS.
- i) Randomization in IWRS will occur after Medical Monitor approval.

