5.3 Lifestyle Guidelines

5.3.1 Contraception Guidelines

Female subjects must be either postmenopausal (absence of menses) for at least 1 year and have menopause confirmed by follicle-stimulating hormone (FSH) levels, or must be postmenopausal for at least 2 years (over 50 years old and absence of menses for 2 years, no confirmation by FSH required), or must be surgically sterile for at least 6 weeks, or must agree to take appropriate precautions to avoid pregnancy from Screening up to and including 105 days after the last dose of cobomarsen or 180 days after the last dose of vorinostat, if of childbearing potential.

Males must agree to take appropriate precautions to avoid fathering a child from Screening up to and including 105 days after the last dose of study treatment and must consent to using an acceptable method of contraception such as a condom and a highly effective second method

(examples provided below), surgical sterilization (by one of the partners), postmenopausal partner (meeting the definition above), or abstinence.

The following methods have been determined to be highly effective (< 1% failure rate per year when used consistently and correctly) ([Trussell 2004](#); [Clinical Trial Facilitation Group 2014](#)) and are permitted under this protocol for use by the subject and his/her partner:

- Complete abstinence from heterosexual intercourse during the entire period of risk associated with the study treatments, when this is in line with the preferred and usual lifestyle of the subject;
- Oral, intravaginal, or transdermal combined (containing estrogen and progestogen) hormonal contraception associated with inhibition of ovulation;
- Oral, injectable, or implanted progestogen-only hormonal contraception associated with inhibition of ovulation;
 - Note: Progestogen-only “mini-pills” are not considered highly effective methods of contraception for this protocol because inhibition of ovulation is not their primary mechanism of action.
- Intrauterine device (IUD);
- Intrauterine hormone-releasing system (IUS)
- Vasectomy or vasectomized partner, provided that the partner is the sole sexual partner of the female trial participant and that the vasectomized partner has received medical assessment of the surgical success;

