- Bilateral oophorectomy with or without hysterectomy or tubal ligation at least 6 weeks prior to taking study treatment. In the case of oophorectomy alone, only when the reproductive status of the woman has been confirmed by follow-up levels of luteinizing hormone, FSH, and/or estradiol.
 - Female subjects who have undergone surgical sterilization by oophorectomy alone will have FSH levels assessed at Screening.

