7 STUDY PROCEDURES

The procedures and assessments that are outlined in this section will be performed at the time points specified by study visit in [Section 8](#) (Randomized Period) and [Section 9](#) (Crossover Period), and summarized in [Appendix A](#) (Schedule of Events (Screening, Randomized Period)),

[Appendix B](#) (On Treatment and Post-Treatment Follow-up – Cobomarsen Group), [Appendix C](#) (On Treatment and Post-Treatment Follow-up – Vorinostat Group), [Appendix D](#) (Screening, Crossover Period) and [Appendix E](#) (Crossover On Treatment and Post-Treatment Follow-up).

Written informed consent must be provided by each subject prior to the initiation of any study procedure or assessment that is not part of standard of care.

As part of the informed consent process, the investigational site personnel will review the study design with the subject and confirm the subject's willingness and ability to participate in the clinical study if they are randomized to receive either cobomarsen or vorinostat, or if they elect to screen for the crossover period.

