7.2.2 Clinical Laboratory Assessments

Blood and urine samples will be collected for the tests listed in [Table 5](#) at Screening and at the time points specified in [Appendix B](#), [Appendix C](#) and [Appendix E](#). Clinical laboratory assessments do not need to be performed on Day 1 if Screening laboratory assessments were performed within 3 days prior to Day 1 and subjects met inclusion/exclusion criteria based on Screening results.

Screening for HIV, hepatitis B, and hepatitis C, will be performed at Screening in the randomized period.

Female subjects who are not surgically sterile, must either have absence of menses for 1 year and have menopause confirmed by FSH levels at Screening, or must be postmenopausal for at least 2 years (over 50 years old and absence of menses for 2 years; no confirmation by FSH required).

Complement (C5a, Bb) testing will be performed on Day 1 and Day 2 only.

A central laboratory will be used for analysis of all blood and urine specimens collected, except for flow cytometry and a concomitant CBC used for calculation of absolute lymphocyte count, which will be performed by the site's local laboratory. At Screening, the central laboratory results will be used by the Investigator to determine the subject's eligibility for the study. Local laboratory results will not be used for eligibility determination, except for flow cytometry and the concomitant CBC used for calculation of absolute lymphocyte count. However, after Screening, results from the site's local laboratory may be utilized if needed for timely review by the Investigator (if central laboratory results are not available). Local site laboratory results obtained during the study will not be captured in the eCRF unless the Investigator determines they are needed to clarify why a treatment decision was made or if an AE was recorded based on the local results.

Additional clinical laboratory tests may be obtained at any time during the study at the Investigator's discretion.

Site-specific handling instructions on the collection of blood and urine samples and their shipment to the central laboratory will be provided in the Laboratory Manual.

Table 5: Summary of Clinical Laboratory Tests

Hematology ^a	Chemistry	Urinalysis	Coagulation	Others
Abs Basophils	Albumin	Bilirubin	aPTT	TSH
Abs Eosinophils	Alkaline phosphatase	Blood	INR	
Abs Granulocytes	ALT	Color	PT	Complement (C5a, Bb)
Abs Lymphocytes	AST	Glucose, Urine		
Abs Monocytes	Bicarbonate	Ketones		

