Abs Neutrophils	Calcium	Leukocytes		For WOCBP:
ANC	Chloride	Nitrite		Serum/urine pregnancy test
Basophils	Cholesterol	pH		
Eosinophils	CK ^b	Protein, Urine		
Hematocrit	C-Reactive Protein	Specific gravity		At Screening in the Randomized Period only:
Hemoglobin	Creatinine			HIV
Lymphocytes	Creatinine clearance (calculated)	Urine Chemistry		Hepatitis B
Mean Corpuscular Hemoglobin	Bilirubin (total and direct)	Myoglobin, Urine		Hepatitis C
Mean Corpuscular Hemoglobin Concentration	Glomerular Filtration Rate	Protein, Urine		
Mean Corpuscular Volume	GGT	Microalbuminuria		For confirmation of menopause only:
Mean Platelet Volume	GLDH ^c	Creatinine, Urine (Enzymatic)		FSH
Monocytes	Glucose	Protein/ Creatinine Ratio, Urine		
Neutrophils	LDH			
Platelets	Magnesium			
RBCs	Phosphorus			
WBCs	Potassium			
	Sodium			
	Total protein			
	Triglyceride			
	Urea (BUN)			
	Uric acid			

Abbreviations: Abs = Absolute; ALT = alanine aminotransferase; ANC = absolute neutrophil count; aPTT = activated partial thromboplastin time; AST = aspartate aminotransferase; BUN = blood urea nitrogen; CK = creatine kinase; GGT = gamma-glutamyl transferase; GLDH = glutamate dehydrogenase; FSH = follicle-stimulating hormone; HIV = human immunodeficiency virus; INR = international normalized ratio; LDH = lactate dehydrogenase; PT = prothrombin time; RBC = red blood cell; TSH = thyroids-stimulating hormone; WBC = white blood cell; WOCBP = women of childbearing potential

^a Hematology will include CBCs performed at the central lab and locally when performed concurrently with the flow cytometry

^b For grade 2 or 3 total CK: measure CK, CK isoenzymes weekly for 3 weeks and if total CK remains \leq the grade which triggered increased monitoring, continue to assess CK, CK isoenzymes along with regularly scheduled clinical chemistry assessments.

^c GLDH will be done as a reflex test if a grade 3 or 4 ALT or AST is observed.

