7.2.2.1 Pregnancy Test

Female subjects of childbearing potential must have a negative serum pregnancy test at Screening and negative urine pregnancy tests on Day 1 and at the subsequent time points specified in [Appendix B](#), [Appendix C](#) and [Appendix E](#).

Female subjects of nonchildbearing potential (see definitions in [Section 5.3](#)) do not require pregnancy tests.

Female subjects who have undergone surgical sterilization by oophorectomy alone will have FSH levels assessed at Screening.

All urine collections for pregnancy tests occurring on dosing days must be performed and assessed prior to study treatment administration. A positive pregnancy test will result in immediate discontinuation of study treatment. All pregnancies in study subjects or in female partners of male study subjects will be followed through to outcome and will be reported on the appropriate eCRFs.

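### Appendix A footnote f, the 9.2.1 FSH bullet and Appendix D footnote h order FSH for women with menses in the last year, the wrong group under 5.3.1, 7.2.2 and 7.2.2.1 (minor)

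*Combined protocol and SAP*

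**What the plan says.** **Schedule text.** Appendix A footnote f, on the FSH row for randomized-period Screening, reads: "Only for women who are not surgically sterile as confirmation of menopause (for subjects whose last menstrual cycle was within the last year". Appendix D footnote h repeats it for crossover Screening. The FSH bullet in 9.2.1 gives the same window, again for women who are not surgically sterile.

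**Body text, natural menopause.** Section 5.3.1 gives two routes to postmenopausal status. One is "postmenopausal (absence of menses) for at least 1 year and have menopause confirmed by follicle-stimulating hormone (FSH) levels". The other is "postmenopausal for at least 2 years (over 50 years old and absence of menses for 2 years, no confirmation by FSH required". Section 7.2.2 repeats both for women who are not surgically sterile; under its first route they "must either have absence of menses for 1 year and have menopause confirmed by FSH levels at Screening". Table 5 lists FSH under the label "For confirmation of menopause only".

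**Body text, oophorectomy alone.** Section 5.3.1 adds a separate use: "Female subjects who have undergone surgical sterilization by oophorectomy alone will have FSH levels assessed at Screening". Section 7.2.2.1 repeats it.

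**Randomized-period visit text.** The FSH line in 8.1 states no menses window and sends the reader to Section 5.3.

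**What depends on the result.** Under 7.2.2.1, "Female subjects of nonchildbearing potential (see definitions in" Section 5.3) need no pregnancy tests. Under 5.3.1, a woman who is neither postmenopausal nor surgically sterile must use contraception.

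**The concern.** The schedule and the body text set opposite conditions on the same test. Both footnotes are restrictive, so they do not simply add a group to the one in 5.3.1. A site working from them would draw FSH from women whose status under 5.3.1 it cannot settle, and would not draw it from women whose status depends on it. Section 13.4 makes the site responsible for following the schedule of procedures, yet here following the schedule breaches 5.3.1 and 7.2.2.

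Two things are at stake. A woman who could have been confirmed postmenopausal may stay on contraception and on urine pregnancy tests every 4 weeks without need. The wording could also lead a site to take a high FSH value as proof of menopause in a woman who menstruated a few months ago.

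**Working it through.** The plan gives no figure to reproduce. The main check sets the rules side by side.

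**Step 1. Who needs FSH, and who is sent for it.** Groups are by time since last menses at Screening, leaving aside the exact 1-year boundary.

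| Group | Route in the body text | FSH needed | FSH ordered by footnotes f and h and the 9.2.1 bullet |
|---|---|---|---|
| 1. Not surgically sterile, under 12 months | No postmenopausal route | No | Yes |
| 2. Not surgically sterile, 12 to under 24 months | 1 year plus FSH | Yes | No |
| 3. Not surgically sterile, 24 months or more, over 50 | 2-year route | No | No |
| 4. Not surgically sterile, 24 months or more, 50 or under | 1 year plus FSH | Yes | No |
| 5. Oophorectomy alone | FSH at Screening (5.3.1, 7.2.2.1) | Yes | No |

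Ordered = {1}. Needed = {2, 4, 5}. The overlap is empty.

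**Step 2. Where the correct rule can still be found.** In the randomized period, 8.1 points to Section 5.3, so the error takes effect only if a site follows footnote f instead. In crossover, 9.2.1 and Appendix D are both wrong. The right rule is then reached only through 7.2.2 or through crossover inclusion criterion 5, which points to 5.3.1. Section 7.2.2 does govern crossover, because Section 7 opens: "The procedures and assessments that are outlined in this section will be performed at the time points specified by study visit in" Sections 8 and 9.

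The waiver in 9.2.1 for tests done within 14 days of Day 1 does not normally remove the misplaced draw, because the End of Treatment panel in 8.4 contains no FSH.

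An illustration: a woman 9 months from her last menses at entry is tested under footnote f when FSH cannot settle her status. If she progresses at the planned vorinostat median PFS of 4 months (12.5.2), she is at 9 + 4 = 13 months or more at crossover Screening. FSH could now settle her status, and the schedule does not order it.

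**Step 3. Burden on a woman left unconfirmed.** Urine pregnancy tests fall on Day 1, Day 29 (Week 5), then every 4 weeks from Week 9. For group 2 the Day 1 test is required in any case, by randomized criterion 9 or crossover criterion 4. With the last scheduled test at Week w, tests after Day 1 = (w − 5)/4 + 1.

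- 4 months on treatment: 4 × 52/12 = 17.3 weeks, last test Week 17, (17 − 5)/4 + 1 = **4**.
- 8 months: 8 × 52/12 = 34.7 weeks, last test Week 33, (33 − 5)/4 + 1 = **8**.
- 52 weeks: last test Week 49, (49 − 5)/4 + 1 = **12**.

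The 4 and 8 months are the planned median PFS for vorinostat and cobomarsen in 12.5.2, used as a rough stand-in for time on treatment. Waiting for confirmation of progression adds about one test. The End of Treatment and follow-up tests are extra in each case. Contraception runs 105/7 = 15 weeks past the last cobomarsen dose, or 180/7 = 25.7 weeks past the last vorinostat dose for women.

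**Step 4. How many women.** This cannot be derived, because the documents give no split by sex or menopausal status. In crossover the ceiling is the women among the 63 planned vorinostat subjects who have confirmed skin progression, elect to cross over and were not already confirmed postmenopausal. Entrants from the PRISM study are outside this, since 9.1 does not re-evaluate them for entry.

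**The case against.** The strongest reply is that the rest of the protocol largely contains the error:

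- The randomized-period visit text is correct, and 7.2.2 states the right rule for Screening.
- Section 7.2.2 lets the investigator obtain additional laboratory tests at any time, so nothing bars an FSH draw in groups 2, 4 or 5.
- The Medical Monitor confirms eligibility before randomization (8.1) and before crossover enrollment (9.2.1).
- Crossover subjects other than PRISM entrants have already been through randomized Screening. If 8.1 and 7.2.2 were followed there, the remaining crossover gap is essentially women who passed 12 months without menses between the two Screenings.
- A misplaced FSH draw is not a separate procedure, because blood is already taken at the same Screening.

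All of this stands, and it makes the point minor. It does not reconcile the texts: the safeguards work only when a site sets aside the schedule wording.

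A reader might infer that women with recent menses will enter the trial as postmenopausal, without contraception or pregnancy testing. The documents do not support that. Section 5.3.1 has no postmenopausal route for a woman under 1 year from her last menses, whatever her FSH. Randomized criterion 9 and crossover criterion 4 require negative serum and urine pregnancy tests at entry for any woman with menses within 2 years. The risk is limited to a site misreading the footnote.

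A reader might also infer, from the superscript on the Appendix D serum pregnancy test row, that footnote h restricts that test too. The superscript may be an artefact of reading the PDF, and the row label already agrees with 7.2.2.1. Narrowing the label to menses within 2 years would drop unconfirmed women in group 4, whom 7.2.2.1 still requires to be tested.

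**Conclusion.** Wrong as written, minor. Three current entries direct FSH confirmation to women for whom 5.3.1 and 7.2.2 do not accept it and omit every group that the body text sends for it, including oophorectomy alone. The crossover period is the weaker part, because its visit text and its schedule are both wrong.

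The consequence is operational: misdirected or missed FSH tests, possibly unneeded contraception, and roughly 4 to 8 urine pregnancy tests after Day 1 per woman left unconfirmed. That range assumes time on treatment near the planned median PFS; 12 applies only to a full 52 weeks and should not be read as typical. The 8-month figure is planned for the randomized cobomarsen arm, and the plan gives no separate PFS assumption for crossover.

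The number of women is unknown and could be zero. No efficacy analysis is affected. The finding on the rules themselves rests on the text alone and needs no assumption.

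**What to change.** In Appendix A footnote f, Appendix D footnote h and the 9.2.1 FSH bullet, delete the sterility and last-menses criterion and state that FSH is drawn when required under Section 5.3, as 8.1 already does. This corrects the menses window and brings in oophorectomy alone.

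Make no change to the Appendix D serum pregnancy test row.

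The cost is two footnotes and one bullet. No new assay is needed, because FSH is already in Table 5.
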